The results of this study may help synthesize complex intraoperative clinical information and unveil novel therapeutic strategies. Derived from data from the QEII Hospitals, the results would be directly applicable to the care of Nova Scotians. The models may lead to the creation of objective risk stratification scores calculated at the end of surgery, to identify high risk patients for increased postoperative follow-up and monitoring. Moreover, if models created using machine learning perform well, machine learning may be used more frequently to reveal the patterns within complex, large perioperative datasets. Hemodynamics are potentially modifiable risk factors. Future research includes prospective studies on whether targeted hemodynamic goals, increased postoperative follow-up of high-risk patients, and real-time machine learning precision medicine could improve outcomes after surgeries.

Specific aims

1. To use machine learning techniques to investigate systematically intraoperative hemodynamic predictors of postoperative 30-day all-cause mortality (primary outcome) and major in-hospital morbidity. Hemodynamic predictors to be studied are blood pressure, heart rate, oxygen saturation, end-tidal carbon dioxide, and medications to adjust blood pressure. Please see “Outcomes” section below for full list of secondary outcomes.
2. To evaluate performance of machine learning models created and compare the performance of the best model to the Surgical Apgar Score.

Hypothesis

Controlling for other predictors, the durations of mean arterial pressure (MAP) <65mmHg, heart rate <60 or >100 beats per minute (BPM), hemodynamic medications use, oxygen saturation (SpO₂) <88%, and end-tidal carbon dioxide (EtCO₂) <30 or >45 will be associated with postoperative 30-day all-cause mortality (primary hypothesis) and 30-day major in-hospital morbidity (secondary hypothesis). Note that blood pressure, heart rate, vasopressors and

inotropic medications, oxygen saturation, and end-tidal are considered key indicators of hemodynamics. We have chosen conventional ranges commonly used in practice, and will perform sensitivity analysis of different definitions of each hemodynamic variable.

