Since intraoperative hemodynamics are automatically recorded and mortality reporting is mandatory, we do not expect significant missing data for the key hemodynamic predictors and primary outcomes. For disease conditions, patients without ICD codes are assumed to not have the disease; the same applies for medications. For the other variables of interest, if there is less than 5% missing data, no processing will be performed. Between 5-20%, missing data will be imputed using group mean (43) for continuous variables. At greater than 20% missing data, the variable will be removed from analysis with potential causes evaluated and reported.

Creating the models

We will divide the cohort temporally (approximately 80:20 ratio) into two groups: derivation/training group (approx. January 1, 2013 – Dec 31, 2016), and validation group (approx. Jan 1, 2017 – December 1, 2017). This temporal approach to the model building vs. validation groups will also mirror the real-life application of machine learning, where data from the past is used to predict future outcomes. Splines will be used for the hemodynamic predictors involving time as a unit.

In the derivation/training set, we will create models for the *primary outcome* using machine learning techniques, including logistic regression with variable selection, classification trees, and Principal Component Analysis (PCA)(21). We have chosen these techniques to obtain interpretable results, i.e. being able to understand the process by which the algorithm decision making occurred. Also, these techniques demonstrate different approaches and perspectives to better understand the relationships amongst the variables.

Logistic regression with variable selection (e.g. LASSO, Elastic Net) identifies the most important predictors to create a parsimonious model. Classification trees predict outcomes based on input variables through classification. Random forest is an ensemble method of classification trees; while it is not directly interpretable, it can show which predictor has the highest importance. Association rule learning will be used to find new patterns. PCA is used for

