The performance of all models created will be evaluated in the validation set as part of internal validation using the same metrics of discrimination, calibration, and risk reclassification, and compared to the Surgical Apgar Score. Since there will likely be significant class imbalance and ROC curves may overestimate model performance, for each model, precision and recall curves (PRC), F score, average precision, and AUC will also be reported and compared. The best performing model will also be used to analyze for predictors for secondary outcomes. Sensitivity (recall, true positive rate), specificity, positive predictive value (precision), G-mean, negative predictive values, False Discovery Rates (FDR), optimism, and measures of association of hemodynamic thresholds for primary and secondary outcomes will be computed. Bayesian network causal inference analysis may be performed, to help increase interpretability.

Sensitivity and subgroup analysis

Sensitivity analysis will be performed for different definitions of hemodynamic derangements. Subgroup analysis will be performed based on age, sex, high preoperative risk (most significant indicator of preoperative comorbidity in Table 2, based on final model), RCRI, frailty (HFRS), preoperative hypertension, a select list of intermediate-high risk, gender-neutral elective surgery (please see Appendix – RCRI Protocol Table 1), emergency surgery, and type of anesthesia.

Power calculation

The 2016-2017 in-hospital mortality after major surgery in Nova Scotia is 1.7% (47). Using the Events Per Variable criterion (EPV) of at least 10 outcomes per predictor in the sample, the 1.7% mortality (408) out of an estimated sample size of 24,000 for the derivation/training group means that our model would be valid for up to 41 predictors for the primary outcome. However, the EPV may over or underestimate the limitations of the EPV criterion (48), square root of the mean squared prediction error (rMPSE) and mean absolute prediction error (MAPE) will be calculated based on the number of predictors, sample size and events fraction (49) with the caveat that this model has not been externally validated. Full power calculation will be performed once we receive the final sample size.

Strengths

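### The tiered missing-data rule (no processing, single group mean, or removal of the variable) can leave residual confounding in the adjusted vital-sign and mortality associations; multiple imputation would serve better

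*Combined protocol and SAP*

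**What the plan says.** The Missing data section gives three tiers for variables other than the key hemodynamics and the primary outcome:

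- Below 5%: "if there is less than 5% missing data, no processing will be performed".
- At 5-20%: "Between 5-20%, missing data will be imputed using group mean (43) for continuous variables".
- Above 20%: "At greater than 20% missing data, the variable will be removed from analysis with potential causes evaluated and reported".

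Two statements limit the scope. The authors write that "we do not expect significant missing data for the key hemodynamic predictors and primary outcomes". For diagnoses, "patients without ICD codes are assumed to not have the disease", and medications are treated the same way.

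The section does not define the group, gives no rule for categorical variables at 5-20%, and does not say how a model treats a row left incomplete. Multiple imputation is not mentioned anywhere. Sensitivity and subgroup analysis covers alternative hemodynamic definitions but not missing data.

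The primary hypothesis is an adjusted one. It begins: "Controlling for other predictors, the durations of mean arterial pressure (MAP) <65mmHg".

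**The concern.** Because the hypothesis is about associations after adjustment, the covariates have to carry the control of confounding. Each tier weakens that control or the sample in a different way:

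- **Single mean.** Patients with a missing confounder all receive one value, so for them the confounder is not adjusted for at all. Part of its effect passes to the exposure.
- **Removal.** The confounder is unadjusted for everyone.
- **No processing.** No confounder is lost, but standard logistic, LASSO and PCA fits need complete rows, so patients and deaths would normally be lost. The same happens to categorical covariates at 5-20%, for which there is no rule.

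The plan itself names an incomplete variable. The baseline clarifications under Data processing and artifact removal say that only some patients have a preoperative HSM blood pressure or heart rate. Appendix 1 ties the absence of HSM pressure to emergency surgery, which is itself a listed risk factor. Missingness of this kind is unlikely to be random.

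**Working it through.** **Inputs from the documents.** Power calculation: "the 1.7% mortality (408) out of an estimated sample size of 24,000 for the derivation/training group", and at least 10 events per predictor. The tier limits are 5% and 20%. The documents give no missingness rates, confounder strengths or correlations, so those below are assumptions.

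**Step 1: the plan's own figure.** 24,000 × 0.017 = 408 deaths; 408 / 10 = 40.8, stated as 41 predictors. It reproduces.

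**Step 2: rows lost below 5%, if fits use complete rows.** With k covariates each missing a fraction m independently, the share retained is (1 − m)^k.

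| k | m | Retained | Patients lost of 24,000 | Deaths left of 408 | Predictors at 10 events each |
|---|---|---|---|---|---|
| 1 | 4.9% | 0.951 | 1,176 | 388 | about 39 |
| 10 | 2% | 0.817 | 4,390 | 333 | about 33 |
| 10 | 4% | 0.665 | 8,044 | 271 | about 27 |
| 10 | 4.9% | 0.605 | 9,478 | 247 | about 25 |

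For example, 0.96^10 = 0.665 and 408 × 0.665 = 271. Overlapping missingness would lose fewer.

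**Step 3: residual confounding at 5-20%.** Logistic simulation with 24,000 patients, 1.7% events, true exposure OR 1.00, one confounder with OR 2.0 per SD, and 60 replicates per setting. Missingness is either completely at random (MCAR) or at random given exposure and outcome (MAR: log-odds of being missing +0.8 per SD of exposure and +1.0 for death). Entries are exposure ORs, the exponential of the mean log-OR.

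| Correlation | Missing | Mechanism | Full data | Overall-mean imputation | Multiple imputation |
|---|---|---|---|---|---|
| 0.3 | 10% | MCAR | 1.00 | 1.02 | 1.00 |
| 0.3 | 10% | MAR | 1.01 | 1.10 | 1.01 |
| 0.3 | 20% | MCAR | 1.00 | 1.05 | 1.00 |
| 0.3 | 20% | MAR | 1.00 | 1.12 | 1.00 |
| 0.5 | 10% | MCAR | 1.02 | 1.06 | 1.02 |
| 0.5 | 10% | MAR | 0.99 | 1.16 | 0.99 |
| 0.5 | 20% | MCAR | 1.00 | 1.09 | 1.00 |
| 0.5 | 20% | MAR | 1.00 | 1.26 | 1.00 |

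The full-data column shows the simulation noise, up to about 0.02. Mean imputation is biased even under MCAR. A weaker confounder (OR 1.5, correlation 0.3, missingness rising with the confounder itself) gave 1.03 at 10% and 1.05 at 20%, inside the same range.

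**Step 4: the other tiers, same simulation (confounder OR 2.0).** Removing the confounder gave 1.22 to 1.43. Complete-case fitting at 4.9% missing gave about 0.94 under MAR, so in that setting the loss is not only one of precision. If the group were the outcome group, 20% missing under MAR gave 1.06 to 1.12.

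**Step 5: missingness that depends on the unseen value.** When missingness rises with the confounder itself (confounder log-OR 1.0 per SD, correlation 0.5), complete-case fitting was nearly unbiased (0.99 to 1.01). Multiple imputation left 1.00 to 1.10, depending on how steeply missingness rises; it was still clearly better than mean imputation.

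**The case against.** The strongest reply is that the rule touches few variables. Diagnoses and medications count as absent when not recorded. Appendix 1 falls back on a diagnosis code when BMI is missing and describes anesthetic type as a mandatory field. Case mix group, service, procedure and ICU status come from the administrative record. By count of Table 2, about ten covariates could be partly missing: HSM blood pressure and heart rate, anesthetic concentration, BIS, temperature, blood loss, hemoglobin, surgical duration and possibly ASA class. Strong confounders such as age, comorbidity and frailty scores and emergency status are largely outside the tiers and partly stand in for the rest. The plan also promises to report causes above 20%, and Limitations concedes unknown confounding. All of this stands, and it limits the size. It does not justify a single mean where a covariate does fall in the tier.

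Four stronger readings are tempting but not supported:

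- **About half the cohort would be lost.** Twenty independent covariates at 3% or 4.9% missing would lose 46% or 63% (1 − 0.97^20; 1 − 0.951^20). The documents leave only about ten candidates and give no rates. Row deletion is also inferred: the plan says no processing, and some tree software keeps incomplete rows.
- **Multiple imputation would abolish the bias.** Step 5 shows it does so only under missing-at-random.
- **The outcome leaks into the predictors.** That holds only if the group is the outcome group. The plan does not say, and the cited source was not available for this review.
- **Intervals are seriously too narrow.** Standard errors under mean imputation were about 0-3% below those from multiple imputation with a moderate confounder, and about 2-11% below with a strong one.

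**Conclusion.** The concern holds in a limited form. Single mean imputation or removal of a confounder can bias the adjusted associations in the primary hypothesis, and nothing elsewhere in the plan offsets this. With a true OR of 1.00, mean imputation gives about 1.02 to 1.26 under the assumptions in the brief; removal gives more. With one or two nearly complete covariates the effect is small. Loss of rows below 5% is a likely consequence of standard software, running from about 20 deaths (408 − 388) to about 137 (408 − 271) in the two cases taken. Confidence is high that the method is weak, and lower on magnitude, because the true missingness is unknown. The undefined group and the missing categorical rule need correcting whatever the size. This is a change that should be made before modelling; it does not invalidate the study.

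**What to change.** **Association models (regression).** Replace the 5% and 20% tiers with multiple imputation by chained equations for every partly missing continuous and categorical covariate. Put the outcome and all predictors in the imputation model, pool by Rubin's rules, and report complete-case analysis as a sensitivity analysis.

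**Prediction models.** Fit the imputation in the derivation set without the outcome and apply it unchanged to the validation set. Where pooling across trees, PCA or resampling is impractical, a single stochastic or model-based imputation is acceptable.

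**In both.** Do not impute by outcome group. Report the percentage missing for each variable. Drop a variable only when it is not recorded by design. Reconcile the 20% rule with the plan to model HSM baselines separately: if more than 20% of patients lack them, the present rule would remove variables that the plan intends to analyse.

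**Cost.** SAP text, more computing and a pooling step that takes real work alongside variable selection. SAS and R, already planned, support it. The change does not address the assumption that no diagnosis code means no disease, and it only reduces bias where missingness depends on the unseen value.

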At the time of surgery, anesthesiologists document the timing of key clinic information (induction, intubation, start and end of surgery, emergence, extubation, and exit of the operating room), medications and fluids administered, estimated blood loss, and type of anesthesia into the intraoperative record. Hemodynamic factors are automatically recorded into the database every minute. The following intraoperative hemodynamic factors will be included in model building:

Table 1. Exposures

Blood pressure	
Since there is no universal definition of low blood pressure under anesthesia, we will use several different variables to determine the most significant exposure by threshold and duration. Both Systolic Blood Pressure (SBP) and Mean arterial pressure (MAP) have been used in blood pressure research (12). In a recent study (26), different blood pressure modeling techniques on the same dataset led to different conclusions on the impact of hypotension on postoperative myocardial infarction and kidney injury. Methods with the largest odds ratios were absolute maximum decrease in MAP and mean episode area under threshold. However, since the area under threshold is less interpretable and difficult to calculate in everyday clinical practice, the duration under threshold will be used.
 
SBP
 
1. Maximum change from preoperative SBP, in a) absolute change (mmHg), and b) relative change (%) (emergency and elective cases analyzed separately due to the lack of preoperative blood pressure in the emergency group)2. Cumulative duration (minutes) $\geq 20\%$ below preoperative SBP3. Longest single episode (minutes) below a) 80, b) 90, and c) 100 mmHg4. Cumulative duration (minutes) below a) 80, b) 90, and c) 100 mmHg 
MAP
 
1. Maximum change from preoperative MAP, in a) absolute change (mmHg), and b) relative change (%) (emergency and elective cases analyzed separately due to the lack of preoperative blood pressure in the emergency group. Note that since the HSM database only contains SBP and DBP, not MAP, MAP will be calculated using $MAP = 1/3*SBP + 2/3*DBP$)2. Cumulative duration (minutes) $\geq 20\%$ below preoperative MAP3. Longest single episode (minutes) below a) 60, b) 65, c) 70, and d) 80mmHg4. Cumulative duration (minutes) below a) 60, b) 65, c) 70, and d) 80mmHg
-----------------------	---

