Heart rate	Since both fast and slow heart rate may be harmful and there is no universal definition of abnormal heart rate under anesthesia, we will model using a variety of methods. 
 1. Maximum change (BPM) from preoperative heart rate (positive and negative) 2. Relative change (%) from preoperative heart rate (positive and negative) 3. Maximum pulse variation (maximum heart rate minus minimum heart rate) 4. Longest single episode (minutes) a) below 60, and b) above 100BPM 5. Cumulative duration (minutes) a) below 60, and b) above 100BPM
Use of hemodynamic medications (i.e. special medications for blood pressure)	
 1. Vasopressor/inotrope use (yes vs. no): phenylephrine, norepinephrine, epinephrine, vasopressin, dobutamine, or milrinone 2. Infusion of any vasopressor/inotropes above (yes vs. no) (identified by unit of weight over time) 3. Phenylephrine/ephedrine bolus (yes vs. no) (identified by unit of weight only) 4. Vasodilator use (yes vs. no): labetalol, esmolol, nitroglycerin, nitroprusside 5. Infusion of any vasodilator above (yes vs. no) (identified by unit of weight over time)
Oxygen saturation by pulse oximetry: SpO₂	
 1. Longest single episode (minutes) below a) 88, and b) 90% 2. Cumulative duration (minutes) below a) 88, and b) 90%
End-tidal (i.e. exhaled) Carbon dioxide: EtCO₂	
 1. Longest single episode (minutes) a) below 30, and b) above 45mmHg 2. Cumulative duration (minutes) a) below 30, and b) above 45mmHg

II. Outcomes

Primary: 30-day all-cause postoperative mortality (binary)

Secondary:

1. Major 30-day in-hospital morbidity, both in terms of the individual category (yes/no), and an overall composite (i.e. yes for any of the 6 categories vs. no). We have included major morbidity outcomes where increased monitoring would be beneficial, using International Statistical Classification of Diseases (ICD) 10 codes and based on published protocol on patient safety indicators (27).
 1. Cardiac: composite of acute myocardial infarction, cardiac arrest, ventricular tachycardia, congestive heart failure, pulmonary edema, complete heart block, shock excluding septic shock
 2. Respiratory: composite of pneumonia, pulmonary embolism, acute respiratory failure, respiratory arrest, Mechanical Ventilation \geq 96 hours
 3. Acute Kidney Injury
 4. Cerebrovascular: composite of strokes and transient ischemic attacks

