 5. Delirium
 6. Septic Shock
2. Postoperative ICU admission (yes/no)
3. Prolonged Postoperative Length of Stay (LOS) (greater than vs. less than or equal to CIHI Expected Length of Stay (ELOS) as assigned by the Case Mix Grouping) [note that the LOS includes the day of surgery]
4. Hospital readmission within 30 days (yes/no)
5. Intraoperative mortality (yes/no)
6. Days alive and out of hospital at 30 days postoperatively (28)

III. Other predictors included into model

The following potential perioperative predictors will be evaluated as covariates during model building. Statistically significant predictors will be retained in the model.

Table 2. Other predictors

Preoperative	
 1. Demographics: age on date of surgery, sex, obesity (body mass index>30) 2. Indicators of preoperative comorbidities: since no comorbidity score has perfect performance, a variety of models will be evaluated and the most significant predictive score will be retained in the model. 
 • American Society of Anesthesiologist class • RCRI score(29), and specific components via ICD codes (history of ischemic heart disease, congestive heart failure, cerebrovascular disease, diabetes, chronic kidney disease, and CCI and Case Mix Group codes of suprainguinal vascular, intraperitoneal, or intrathoracic surgery) using previously published methods (30)(31) • Elixhauser comorbidity index (32) and Charlson Comorbidity Index (33): calculated using diagnoses from the previous three years according to standard algorithm by HDNS. Reported as both total score and individual categories • Hospital Frailty Risk Score (34): based on ICD codes • Preoperative blood pressure: ICD diagnosis of hypertension and by measured blood pressure • Preoperative heart rate: Innovian and HSM • Chronic Obstructive Lung Disease (ICD code): since it may affect the interpretation of results of SpO₂ and EtCO₂ 3. Indicators of surgical complexity 
 • CIHI DAD Case Mix Group (CMG) class (also contains categories that include medical complexity) • Main Surgical Service • Procedural Index for Mortality Risk (PIMR) (35): according to CCI • Procedure: CCI codes • Preoperative ICU admission • Emergency surgery: as determined by DAD Method of Entry = emergency department or transferred from another institution)

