This study involves a large, recent population dataset with nearly complete follow up for the primary outcome. There has been more than 10 years of experience with intraoperative anesthetic electronic recording system, with a high likelihood of provider proficiency with anesthetic intraoperative electronic documentation. This dataset is unique in North America for its degree of intraoperative details, pairing of clinical and administrative data, and robust data quality. Our use of machine learning could detect new network relationships and strategies that may inform current practice as well as future research.

Limitations

This study involves two academic provincial adult non-obstetric tertiary care centres in one hospital system, which may represent a sicker population. Validation in other centres would

increase generalizability. The retrospective nature of this database study makes it susceptible to random error, bias, and confounding. There may be cluster effects from health providers and hospitals, however the large sample size allows for robust power and minimizes random error. There is a potential for misclassification, measurement, and ascertainment bias. Due to the lack of universal screening for morbidity (e.g. troponin biomarker for myocardial injury and infarction, and Brain-Natriuretic Peptide for preoperative cardiac risk stratification), only mortality will be included as primary outcome. The lack of postoperative hemodynamic data creates non-informative censoring (i.e. unbiased since the data is missing for all patients). Numerous other predictors have been adjusted for through multivariate logistic regression but unknown confounders and confounding by indication may remain. The retrospective data reflects a snapshot of evolving practice, though secular effects may remain limited over the five-year study period. Future prospective validation of the prediction model will increase external validity.

Future directions

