Appendix 1. Summary of Variables

Source Dataset	Variable	Level of Identification	Time Span	Why is this element required in the analysis?
Information for inclusion and data linkage				
Innovian	Date of surgery	Patient	Jan 1, 2013 to Dec 1, 2017	
Part of HDNS data linkage with Innovian to ensure only variables from the surgical admission of interest (first surgery admission with LOS>1) is included. This Date of Surgery will be used to confirm linkage with “PDATE” from CIHI DAD to ensure that data from the correct surgical admission is included. The maximum allowable mismatch for the surgery dates in Innovian and CIHI is +/- 1 day. The Innovian surgery date will be used as the gold standard, since the record is done in real time and thus the most accurate.
 
The date of surgery will also be used to divide the cohort temporally into the derivation/training group (January 1, 2013 – November 30, 2016), and validation group (December 1, 2016 – December 1, 2017)

Innovian	Patient_ID: encrypted health card number	Patient	Jan 1, 2013 to Dec 1, 2017	HDNS data linkage with Innovian. The dataset given to us will not contain Patient_ID, but rather a Study ID.
Innovian	Age: on date of surgery	Patient	Jan 1, 2013 to Dec 1, 2017	Age ≥ 45 part of inclusion criteria. Also, as age may impact outcomes, this will be included as a covariate in our models
Innovian	Organ donation: Procedure name	Patient	Jan 1, 2013 to Dec 1, 2017	Patients with procedure name that includes “organ donor” or “organ donation” will be excluded, since they are already declared brain dead and

	containing the word “Organ donor” or “Organ donation” or “DCD” [Derived by Innovian]			will not reflect the usual surgical population.
Innovian	Cardiac surgery [Derived by Innovian]	Patient	Jan 1, 2013 to Dec 1, 2017	As defined by ProcedureAnatomy = “heart” or “cardiac”. Cardiac surgery patients are excluded since they are receiving surgery directly on the heart and have a unique set of complications that may not reflect the usual surgical population.
Innovian	ASA: American Society of Anesthesiologist class (I to VI)	Patient	Jan 1, 2013 to Dec 1, 2017	Patients with ASA VI (i.e. patient with neurologic brain death for organ donation) will be excluded. Also, as this may affect outcomes, it will be included as a covariate in our models.

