Innovian	SpO₂: Oxygen saturation by pulse oximetry [Derived by Innovian as multiple variables – see right]	Patient	Jan 1, 2013 to Dec 1, 2017	
Exposure variable to be included into modeling. The following variables will be derived by Innovian:
 
3. Longest single episode (minutes) below a) 88, and b) 90%
 
4. Cumulative duration (minutes) below a) 88, and b) 90%

Innovian	EtCO₂: End-tidal (i.e. exhaled) [Derived by Innovian as multiple variables – see right]	Patient	Jan 1, 2013 to Dec 1, 2017	
Exposure variable to be included into modeling. The following variables will be derived by Innovian:
 
1. Longest single episode (minutes) a) <35, and b) >45
 
2. Cumulative duration (minutes) below a) <35, and b) >45

HSM	Duration of surgery	Patient	Jan 1, 2013 to Dec 1, 2017	As this may affect outcomes, it will be included as a covariate
Innovian	Type of anesthesia	Patient	Jan 1, 2013 to Dec 1, 2017	Categorical variable: general, neuraxial, peripheral nerve block, and/or managed anesthesia care [i.e.

				
sedation] – multiple concurrent possible). As this may affect outcomes, it will be included as a covariate.
 
Innovian will be used instead of the CIHI ANATYP (Anaesthetic Type), since anesthetic type is a mandatory field in Innovian and will allow for multiple concurrent anesthetic types.

Innovian	Average MAC-adjusted: Minimal Alveolar Concentration adjusted by age [Derived by Innovian]	Patient	Jan 1, 2013 to Dec 1, 2017	Age-adjusted MAC will be calculated by Innovian from the end-tidal % of all inspired volatiles according to published protocol (36). The MAC, available every 15 seconds will be averaged (i.e. time-averaged MAC). The averaged MAC will be included as a covariate.
Innovian	BIS : Bi-spectral Index [Derived by Innovian]	Patient	Jan 1, 2013 to Dec 1, 2017	Duration in minutes for BIS <46. As deep anesthesia (low BIS) may affect outcomes (50), it will be included as a covariate.
Innovian	Laparoscopy-booked [Derived by Innovian]	Patient	Jan 1, 2013 to Dec 1, 2017	Binary variable (yes/no), as defined by “laparoscope” or “laparoscopic” in procedure name.
DAD	Laparoscopy converted to open flag STATUS[1-n] [Flag by HDNS]	Patient	Jan 1, 2013 to Dec 1, 2017	
Flag: STATUS[1-n] = C “Converted from endoscopic to open”
 
Since Innovian procedure names are usually from OR booking, procedures where laparoscopy was converted to open would be included in the laparoscopy (booked) variable.

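### Splines are specified only for the hemodynamic minutes; surgery duration has no stated form, so a curved duration effect, if entered linearly, can appear as a hemodynamic association.

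*Combined protocol and SAP*

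**What the plan says.** The primary hypothesis concerns adjusted associations with 30-day mortality: "Controlling for other predictors, the durations of mean arterial pressure (MAP) <65mmHg", followed by the other hemodynamic ranges. Table 1 builds these exposures as raw minutes, either longest episode or cumulative. It explains the choice over area measures: "since the area under threshold is less interpretable and difficult to calculate in everyday clinical practice, the duration under threshold will be used".

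On functional form, the section on creating the models says only "Splines will be used for the hemodynamic predictors involving time as a unit". Knots and degrees of freedom are not given.

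Surgery duration appears in Table 2 and in Appendix 1 ("Duration of surgery", sourced from HSM) as a covariate, with no transformation or spline. Age is treated the same way ("as age may impact outcomes, this will be included as a covariate in our models"). Of the Table 2 covariates generally, the plan says "Statistically significant predictors will be retained in the model". The Limitations section describes the adjustment as regression-based: "Numerous other predictors have been adjusted for through multivariate logistic regression".

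**The concern.** Time spent below or above a threshold can only build up while the patient is monitored, so longer cases tend to have more exposure minutes. Case length is also a plausible marker of risk in its own right. That makes duration the covariate most closely tied to these exposures by construction.

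The plan's rule gives the exposure a flexible curve and says nothing about the confounder. If duration enters as a straight line and its true effect is curved, the line leaves residual confounding, and a correlated, flexible exposure term can absorb it. The result would be an apparent harmful range of minutes that reflects long or short operations. This bears on the study's main claim, which is that the minutes matter after adjustment. Retention by significance adds a second route to the same problem, because duration could be dropped altogether.

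**Working it through.** **The plan's own figure.** The power calculation gives 24,000 derivation patients and 1.7% mortality: 24,000 × 0.017 = 408 deaths. At 10 events per predictor, 408 / 10 = 40.8, stated as 41. This reproduces.

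**What the rule already costs.** Table 1 has 28 predictors measured in minutes: SBP 7, MAP 9, heart rate 4, SpO₂ 4, EtCO₂ 4. A restricted cubic spline with k knots uses k − 1 parameters. Splining all 28 takes 28 × 2 = 56 parameters at 3 knots or 28 × 3 = 84 at 4 knots, both above 41 before any covariate is added.

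**Null simulation.** From the documents: N = 24,000 and 1.7% deaths. Everything else is assumed:
- surgery duration D lognormal, median 120 min, log-SD 0.6;
- exposure minutes = D × a Beta-distributed share with no effect on death: Beta(1,6), mean 1/7 = 14%, correlation with D 0.54; or Beta(3,9), mean 3/12 = 25%, correlation 0.75;
- a linear age effect;
- log-odds for duration: linear 0.004·D; mild log 0.4·ln(D/120); stronger log 0.7·ln(D/120); plateau 0.006·min(D, 240); or a U-shape in ln D.

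The test is a 3-df likelihood-ratio test of a 4-knot exposure spline at 5% (the documents state no alpha), with 150 runs per setting. The Monte Carlo standard error is √(0.05 × 0.95 / 150) ≈ 2 points near 5% and √(0.5 × 0.5 / 150) ≈ 4 points near 50%.

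False-positive rate, duration linear → duration splined:

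| True duration effect | Correlation 0.54 | Correlation 0.75 |
|---|---|---|
| Linear | 2% → 2% | 4% → 5% |
| Mild log | 5% → 6% | 17% → 5% |
| Stronger log | 13% → 7% | 50% → 5% |
| Plateau | 17% → 5% | 57% → 7% |
| U-shape | 70% → 8% | 98% → 5% |

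With both duration and exposure linear, the rate was 3-9% across the ten settings. The inflation therefore comes from pairing a flexible exposure with a rigid duration term.

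**Sensitivity to the assumptions** (log and plateau duration effects unless stated, linear → splined):
- Beta(2,5), mean share 2/7 = 29%, 300 runs: 38% → 5% (log) and 42% → 7% (plateau); with a linear duration effect, 7% → 6%. A separate set of 150 runs gave 46-49% → 4-5% for the two curved shapes.
- Beta(0.8,5), mean share 14%: about 15% → 5-7%.
- Beta(0.8,5), half the patients at zero minutes, plus two covariates correlated with duration: 7-9% → 7%.
- Sparse exposure, Beta(0.5,20), half at zero: 4-5% → 3-5%.
- Monitoring window longer than the duration covariate: 20-33% → 4-8% when exposure took a large share of the case, about 7% → 3% when sparse, and no penalty for splining when the duration effect was linear.

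**The case against.** The strongest reply is that the plan never says duration is linear. That is right: the form is unstated, and linear entry is an inference. It is still the likely default. The section on data processing says new variables come from calculation or dichotomization as listed in the variables section and Appendix 1, and neither lists a transformation for duration.

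Second, the inflation is conditional. It needs real curvature and a substantial correlation between minutes and duration, and the documents give neither. With sparse exposure, or with other duration-related covariates in the model, it largely disappears. Blood loss, crystalloid, transfusion and procedure are such candidates in Table 2. The simulations also test one exposure without a penalty, which is not the LASSO procedure itself. All of this stands and limits the size of the claim. It does not remove the asymmetry.

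Third, classification trees and random forest impose no straight line on any predictor. This also stands; the point concerns the logistic models.

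A reader might go further in several ways that the documents do not support:
- **That minutes can never exceed the duration covariate.** Exposures are taken between the first and last valid SpO₂, while the covariate comes from HSM, so a strict bound is not established. The runs with a longer window show that the effect survives this, at a smaller size.
- **That the minutes depend on age.** No passage shows it, and age was not simulated with a curved effect.
- **That heart-rate changes in both directions are forced onto one line.** Table 1 does say "Since both fast and slow heart rate may be harmful", but it lists positive and negative changes and has separate predictors for minutes below 60 and above 100.
- **That every change-from-baseline predictor must be splined, or that group LASSO is required.** These are trade-offs against the 41-predictor limit, and the plan names LASSO and Elastic Net only as examples.

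**Conclusion.** The point holds in conditional form. The plan gives flexibility to the exposure minutes and specifies none for surgery duration, the covariate they accumulate with. If duration is entered linearly in the logistic models, a curved duration effect can show up as a hemodynamic association. Under the assumed distributions, the false-positive rate for a null exposure runs from about 5% (linear or mildly curved duration effect, or sparse exposure) to 20-50% or more (log or plateau effect with exposure a large share of case time). The mildly curved case stays near 5% only at the lower correlation; at 0.75 it reached 17%. A U-shaped effect gave still higher rates, but nothing in the documents points to that shape. Splining duration returns the rate to about 5-8% and loses nothing when the effect is linear.

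The real rate in this cohort cannot be stated, because the documents report neither the distribution of case length nor that of the exposure minutes. The change is worth making because it protects the primary hypothesis at small cost. It does not invalidate the study.

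**What to change.** Extend the spline sentence along these lines: *Restricted cubic splines with 4 knots will be used for hemodynamic predictors measured in minutes. Duration of surgery (HSM) and age will also enter every logistic model of a hemodynamic exposure as 4-knot restricted cubic splines, and will be kept regardless of statistical significance.* In LASSO or Elastic Net, that means leaving the duration and age terms unpenalised. Age is included as ordinary good practice; the evidence above concerns duration.

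Cost: SAP wording and routine R code. A 4-knot spline uses 3 parameters where a line uses 1, so the two covariates add 2 × 2 = 4 parameters. Under the plan's own rule that takes 4 × 10 = 40 of the 408 expected deaths. This is small beside the 56 to 84 parameters that the exposure splines could use, but it should be counted in the same prespecified total. Trees and random forest need no change.
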